1.0 Specific Aims and Major Rational

The primary aim of this mechanistic, double-blind, placebo-controlled proof-of-concept clinical trial is to demonstrate that preemptive oral administration of cocoa flavanol for five days before surgery (equivalent to 50 grams of dark chocolate per day) will attenuate the surgery-evoked increase of HMGB1 in blood plasma and NFkB signaling in innate immune cells shortly after surgery. The HMGB1-NFkB signaling axis is a major pro-inflammatory axis that is activated in response to tissue trauma. Preemptive attenuation of this axis in multiple animal injury models is associated with reduced tissue damage and increased survival. A secondary aim is to capture preliminary patient-centered outcomes data including postsurgical pain and daily functioning for six weeks after surgery, and relate these outcomes to the intake of oral cocoa flavanol and surgery-evoked activation of the HMGB1-NFkB signaling axis.

The protocol for this trial is embedded in previous studies by Drs. [name] and [name] that examined immune correlates of surgical recovery in patients undergoing major joint replacements.^{1,2} These studies have demonstrated that exaggerated activation of NFkB-signaling in innate immune cells in response to surgery predicts delayed resolution of pain and delayed functional recovery after surgery.

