2.0 Background and Rational

Over 40 million major surgeries are performed annually in the US alone, while over 250 million surgeries are performed worldwide.^{3,4} Recovery after surgery is highly variable and can take much longer than expected. For example, patients undergoing major abdominal surgery can take more than six months to fully recover.⁵ Protracted recovery can affect up to 30% of patients and leads to impaired daily functioning, delayed return to work, decreased quality of life, and major socioeconomic costs.⁶⁻⁸ Reducing "loss of productivity" by one day per major surgery could save the US \$8 billion per year for this direct cost alone.⁹

[figure not shown]
During the last two decades significant effort has been made to enhance recovery after surgery.¹⁰ Despite the implementation of pragmatic and standardized clinical protocols to enhance recovery and shorten hospital length of stay, the utility of these protocols for improving patient-centered recovery cost-effectively remains uncertain.¹¹⁻¹³ Critical elements of recovery that greatly matter to patients and health care providers include the resolution of pain, daily functioning, and loss of postoperative fatigue.¹⁴ A patient-centered and cost-effective focus on postoperative recovery pays tribute to three goals of health care: Improving patients' experience, improving health, and constraining per capita cost.¹⁵ As such, novel and cost-effective strategies are greatly needed to accelerate patient-recovery after surgery.

Preliminary data by [name] and his collaborators indicate that administration of a cocoa flavanol extract that is equivalent in dose to the amount of cocoa flavanol contained in about 50 grams of dark chocolate decreases plasma levels of HMGB1. HMGB1 is an archetypical alarmin, i.e., an endogenous mediator that is released upon cellular stress and injury. HMGB1 triggers a pro-inflammatory cascade by binding to toll-like receptors (TLRs) on innate immune and other cells, which results in activation of pro-inflammatory transcription factors (e.g. NFkB) and the subsequent release of major pro-inflammatory cytokines (e.g. TNF α). The prominent role of the HMGB1-TLR axis in inflammatory disease states including surgery, trauma, stroke, and myocardial infarction has recently been highlighted.¹⁶⁻¹⁹ Importantly, dampening activity along this pathway in preclinical injury models has been shown to improve outcomes.²⁰⁻²²

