The potential of HMGB1 as a therapeutic target in acute inflammatory disease states has recently been emphasized.^{23,24} A major challenge is the identification of effective and non-toxic clinical strategies that can safely modulate HMGB1 in humans. This research study will evaluate a safe, highly scalable, and relatively cheap pre-surgical nutritional intervention that has significant potential to do just that, safely modulate HMGB1 and improve clinical recovery after surgery. As such, this proposed research could change clinical practice within years. While studied intervention targets a specific pro-inflammatory pathway implicated in aggravated tissue damage and delayed healing/recovery, the use of broader and less specific anti-inflammatory interventions in the perioperative period including non-steroidal anti-inflammatory drugs and corticosteroids is common clinical practice.

Preliminary data

Drs. [name] and [name] have studied immune correlates of clinical recovery in patients undergoing hip replacement surgery.^{1,2} They have successfully implemented mass cytometry at the "bedside" to characterize the immune response to surgery close to invivo conditions in peripheral whole blood of patients.²⁵ These studies have been critically supported by our surgeoncollaborator [name] (coinvestigator). In close collaboration with [name] (co-investigator),

[figure not shown]

the team of investigators has developed computational algorithms that allow extracting biologically meaningful and actionable immune parameters from generated high-dimensional data sets.²⁶

Pertinent to this application are data demonstrating that exaggerated signaling in innate immune cells downstream of toll-like receptor 4 (TLR4) shortly after surgery predicts delayed functional recovery and resolution of pain in patients undergoing hip replacement surgery (Figure 1).^{1,2} TLR4 is a major target of HMGB1, which is massively released by tissue trauma.

Data by our collaborator [name] (coinvestigator) demonstrate that oral administration of a high-dose (1,000 mg) versus a very low dose (10 mg control) of coco-flavanol (CocoaVia[®]) in 24 healthy adults (age 50-70 years) significantly suppressed plasma levels of HMGB1 (Figure 2).

Taken together the preliminary data support the main hypothesis that the preemptive administration of cocoa flavanols in patients undergoing surgery will decrease plasma

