Page 4 Protocol Version # 1 levels of HMGB1, attenuate signaling activity in innate immune cells downstream of TLR4, and accelerate clinical recovery in patients undergoing joint arthroplasty.

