4.0 Materials and Methods

The proposed study is designed as a randomized, controlled, and double-blind study comparing a daily dose of cacao flavanol versus placebo. Cocoa flavanol is commercially available as a nutrient (CocoaVia®), manufactured by Mars Inc. CocoaVia® is supplied in 125 mg capsules

containing 15% epicatechin, the active anti-inflammatory ingredient. Based on our preliminary data a daily oral dose of 1,000 mg will be used in this study.

After participants have completed the informed consent process they will be randomized to one of two treatment groups - half to group A and half to group B. Group A participants will receive a daily oral dose of 1,000 mg cocoa flavanol (CocoaVia®) for 5 days before surgery, while group B participants will receive a daily oral dose of a placebo for 5 days before surgery.

Patients will be involved in study procedures from the time they consent to participate through postoperative week 6. Procedures to evaluate baseline condition, hospital course, and recovery will take place as follows:

Questionnaires: Before hospitalization participants will complete questionnaires to evaluate expectations prior to surgery (patient expectations), stress level (perceived stress scale), pain and function (WOMAC), anxiety (POMS-anxiety scale), and baseline fatigue and functional impairment (surgical recovery scale; SRS). Participants will complete SRS and WOMAC scales daily while they are in the hospital, and weekly following discharge to track recovery over a sixweek course.

Objective measures of function: Physical function will also be measured objectively by directly monitoring participant activity using a wearable device (ActiGraph) providing measurements for physical activity/function and sleep. Participants will be asked to wear the device beginning 1 week before surgery through postoperative week 6.

Blood draws: Blood will be drawn at 4 time points; once before administration of the study intervention (40ml), 1 hour before surgery (30ml), 1 hour after surgery (30ml), and on post-op day 1 (30ml). Blood will be processed for analysis of cell signaling with mass cytometry (NFkB in innate immune cells), HMGB1 plasma concentrations, and epicatechin (flavanol) plasma concentrations. Blood samples will be identified using a study code, and will be analyzed in labs at Stanford University and Stanford Health Care (Stanford Hospital).

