5.0 Statistical Measures

5.1 Outcome Measurements

The primary outcome is the cumulative NFkB signal in innate immune cells 1 and 24 hours after surgery.

Secondary outcomes include HMGB1 plasma levels, functional recovery trajectories (measured objectively with ActiGraph and subjectively with WOMAC function sub-scale), postoperative pain resolution (measured with WOMAC-pain subscale), and postoperative resolution of fatigue and resulting impairment of daily activities (measured with SRS). Trajectories will be reflected by the time to resolve function to mild impairment, the time to resolve pain to mild levels, and the time to resolve fatigue to 50% of maximum postoperative fatigue.

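### The primary aim promises to show an effect on both HMGB1 and NFkB, but only NFkB is a primary, powered outcome; HMGB1 needs a matching aim, one named summary and a baseline-adjusted analysis

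*Combined protocol and SAP*

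**What the plan says.** Section 1.0 gives one primary aim covering two markers: the intervention "will attenuate the surgery-evoked increase of HMGB1 in blood plasma and NFkB signaling in innate immune cells shortly after surgery". Section 2.0 supports the HMGB1 half with the investigators' own cocoa data. It says that an extract equivalent in dose to the "cocoa flavanol contained in about 50 grams of dark chocolate decreases plasma levels of HMGB1", and that in 24 healthy adults the high dose, compared with a very low dose, "significantly suppressed plasma levels of HMGB1 (Figure 2"). The main hypothesis at the end of that section puts HMGB1 first: "the preemptive administration of cocoa flavanols in patients undergoing surgery will decrease plasma" "levels of HMGB1, attenuate signaling activity in innate immune cells downstream of TLR4", followed by faster clinical recovery.

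Section 5.1 is narrower: "The primary outcome is the cumulative NFkB signal in innate immune cells 1 and 24 hours after surgery". HMGB1 plasma level is listed there as a secondary outcome, alongside the ActiGraph, WOMAC and SRS outcomes. Section 5.2 gives the primary outcome an unpaired t-test, gives the secondary outcomes a comparable analysis labelled exploratory, and says that the study is powered for the primary outcome. Section 5.3 sizes the trial on NFkB alone.

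Section 4.0 schedules four draws, two before surgery ("once before administration of the study intervention (40ml), 1 hour before surgery (30ml")) and two after ("1 hour after surgery (30ml), and on post-op day 1 (30ml")), and lists HMGB1 among the assays. No section assigns a draw, a reference value or a summary to the HMGB1 outcome.

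**The concern.** The aim claims more than the plan tests. A significant NFkB result would support the NFkB half of the aim only. The HMGB1 half would rest on an exploratory comparison whose definition is still open. Readers will look for that half, because HMGB1 is the marker for which the protocol cites its own cocoa flavanol data.

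The open definition matters because the aim concerns a surgery-evoked increase, and an increase needs a pre-surgery reference. With two pre-surgery and two post-surgery draws, the analyst could compare a single post-surgery level, a combined level, or a change from either pre-surgery draw. These answer different questions. If flavanol lowers resting HMGB1, the post-surgery level can differ between groups although surgery raised HMGB1 equally in both. A summary chosen after the data are seen could present that as a smaller response to surgery.

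The plan also leaves precision unused: an HMGB1 value before the intervention can be had from a scheduled draw, and the implied t-test ignores it.

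**Working it through.** **Aim and outcomes side by side**

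| | NFkB | HMGB1 |
|---|---|---|
| In the primary aim (1.0) | yes | yes |
| Outcome rank (5.1) | primary | secondary |
| Times and summary (5.1) | 1 and 24 hours, cumulative | none stated |
| Analysis (5.2) | unpaired t-test | comparable, exploratory |
| Basis of sample size (5.3) | yes | no |

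**Inputs.** From the documents: 16 per group, significance at 0.05, an unpaired t-test and about 80% power (5.2, 5.3). Assumed: two-sided testing, HMGB1 effects of 0.5, 0.75 and 1 SD, and baseline correlations of 0 to 0.7. The readable text gives no HMGB1 effect size or SD.

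**The plan's own figure.** With n per group and effect d in SD units, the t-test has 2n − 2 degrees of freedom and noncentrality d × √(n/2). Section 5.3 assumes d of about 2. At n = 16 the noncentrality is 2 × √8 = 5.66 on 30 degrees of freedom, against a critical value of 2.042, so power is 99.98% and not about 80%. At d = 1 the noncentrality is 2.83 and power is 78%, close to the stated figure. That discrepancy concerns NFkB and is a separate matter. Here it shows only that 16 per group has roughly 80% power for a 1 SD effect.

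**Level of HMGB1: t-test against ANCOVA.** ANCOVA on the pre-intervention value, at correlation ρ, shrinks the residual SD by √(1 − ρ²) and leaves 32 − 3 = 29 degrees of freedom. At ρ = 0.5 the factor is √0.75 = 0.866, so a 1 SD effect acts like 1/0.866 = 1.15 SD. Power at 16 per group (t-test exact, ANCOVA simulated):

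| Analysis | 0.5 SD | 0.75 SD | 1 SD |
|---|---|---|---|
| Unadjusted t-test | 28% | 54% | 78% |
| ANCOVA, ρ = 0 | 27% | 52% | 77% |
| ANCOVA, ρ = 0.3 | 29% | 56% | 80% |
| ANCOVA, ρ = 0.5 | 34% | 64% | 87% |
| ANCOVA, ρ = 0.7 | 47% | 81% | 96% |

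Simulated type I error was about 0.05. A useless covariate costs about 1 point; at ρ = 0.5 the gain is about 6 to 11 points.

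**Level or rise.** Assume correlation 0.5 among the pre-intervention, 1 hour pre-surgery and post-surgery values, each with SD 1. The change from the 1 hour pre-surgery draw then has SD √(2 × (1 − 0.5)) = 1. Share of simulated trials with a significant result, 16 per group:

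| True effect of flavanol | ANCOVA on level | Change from 1 hour pre-surgery |
|---|---|---|
| Lowers resting level by 1 SD, same surgical rise | 87% | 5% |
| Lowers surgical rise by 1 SD, same resting level | 87% | 78% |

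The level ANCOVA gives the same answer in both cases. Only the change from the 1 hour pre-surgery draw tells them apart.

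**The case against.** The best defence is that the plan already states its hierarchy. NFkB is primary, HMGB1 is secondary and exploratory, and power is claimed for the primary outcome only. Section 1.0 describes a single HMGB1-NFkB axis and Section 2.0 places NFkB downstream of HMGB1, so one downstream readout is a coherent primary outcome for a proof-of-concept trial. That stands. A reader might infer that the primary test is flawed, or that the trial spends type I error on two markers. The documents support neither inference: there is one primary test, and no confirmatory HMGB1 claim is planned in Section 5.

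The HMGB1 definition can also be partly inferred. The aim refers to the period soon after surgery, only two post-surgery draws exist, and Section 5.2 points back to the NFkB analysis. This narrows the choice but does not settle it. The NFkB summary is called cumulative without saying whether that means a sum, a mean or an area, so copying it to HMGB1 would carry over the ambiguity. Nor does the NFkB analysis name a pre-surgery reference that HMGB1 could borrow.

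A reader might further infer that HMGB1 must become co-primary or be formally tested after NFkB. Nothing in the documents requires that. Gating is one option, and it would bar a formal HMGB1 test whenever NFkB missed.

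Finally, the power figures rest on assumed effects and correlations. They measure what the covariate is worth, not the size of the mismatch, which is a matter of wording.

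**Conclusion.** The point holds as a cheap improvement. The primary aim covers two markers, the plan has a primary, powered test for one of them, and the HMGB1 outcome lacks a draw, a reference and a summary. The alpha and power of the NFkB test do not change.

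For the HMGB1 level, ANCOVA is the better method unless the baseline correlation is close to zero, and even then it loses only about 1 point. It does not rescue small effects: at 0.5 SD, power is 27% to 47% over correlations of 0 to 0.7. It would be tempting to read a significant level ANCOVA as proof of a smaller surgery-evoked increase. The two scenarios above show why that does not follow.

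The text comparison rests on no assumption. The power and scenario figures depend on the assumed effects, the assumed correlations, two-sided testing and 16 evaluable patients per group.

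**What to change.** 1. Reword the primary aim in Section 1.0 to NFkB, with HMGB1 as the key secondary outcome.
2. In Section 5.1, name one HMGB1 summary outright, for example the mean of the 1 hour post-surgery and post-op day 1 values. State whether the target is the post-surgery level or the surgery-evoked rise.
3. For the level, replace the unadjusted t-test in Section 5.2 with ANCOVA on the pre-intervention value.
4. If the wording about a surgery-evoked increase stays, let the between-group difference in change from the 1 hour pre-surgery draw carry that claim. Note in the text that this draw is taken after dosing, so it is not an untreated baseline.

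Optional: if a formal HMGB1 claim is wanted, test the one named analysis at two-sided 0.05 only after NFkB is significant at two-sided 0.05. This fixed sequence keeps the error over the two tests at or below 0.05 and takes nothing from NFkB. The HMGB1 powers above are then upper bounds, since NFkB must pass first. Otherwise keep HMGB1 exploratory; steps 1 to 4 still apply.

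Cost: protocol wording and one degree of freedom for the covariate. All draws are already scheduled and no extra patients are needed.

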2.0 Background and Rational

Over 40 million major surgeries are performed annually in the US alone, while over 250 million surgeries are performed worldwide.^{3,4} Recovery after surgery is highly variable and can take much longer than expected. For example, patients undergoing major abdominal surgery can take more than six months to fully recover.⁵ Protracted recovery can affect up to 30% of patients and leads to impaired daily functioning, delayed return to work, decreased quality of life, and major socioeconomic costs.⁶⁻⁸ Reducing "loss of productivity" by one day per major surgery could save the US \$8 billion per year for this direct cost alone.⁹

[figure not shown]
During the last two decades significant effort has been made to enhance recovery after surgery.¹⁰ Despite the implementation of pragmatic and standardized clinical protocols to enhance recovery and shorten hospital length of stay, the utility of these protocols for improving patient-centered recovery cost-effectively remains uncertain.¹¹⁻¹³ Critical elements of recovery that greatly matter to patients and health care providers include the resolution of pain, daily functioning, and loss of postoperative fatigue.¹⁴ A patient-centered and cost-effective focus on postoperative recovery pays tribute to three goals of health care: Improving patients' experience, improving health, and constraining per capita cost.¹⁵ As such, novel and cost-effective strategies are greatly needed to accelerate patient-recovery after surgery.

Preliminary data by [name] and his collaborators indicate that administration of a cocoa flavanol extract that is equivalent in dose to the amount of cocoa flavanol contained in about 50 grams of dark chocolate decreases plasma levels of HMGB1. HMGB1 is an archetypical alarmin, i.e., an endogenous mediator that is released upon cellular stress and injury. HMGB1 triggers a pro-inflammatory cascade by binding to toll-like receptors (TLRs) on innate immune and other cells, which results in activation of pro-inflammatory transcription factors (e.g. NFkB) and the subsequent release of major pro-inflammatory cytokines (e.g. TNF α). The prominent role of the HMGB1-TLR axis in inflammatory disease states including surgery, trauma, stroke, and myocardial infarction has recently been highlighted.¹⁶⁻¹⁹ Importantly, dampening activity along this pathway in preclinical injury models has been shown to improve outcomes.²⁰⁻²²

The potential of HMGB1 as a therapeutic target in acute inflammatory disease states has recently been emphasized.^{23,24} A major challenge is the identification of effective and non-toxic clinical strategies that can safely modulate HMGB1 in humans. This research study will evaluate a safe, highly scalable, and relatively cheap pre-surgical nutritional intervention that has significant potential to do just that, safely modulate HMGB1 and improve clinical recovery after surgery. As such, this proposed research could change clinical practice within years. While studied intervention targets a specific pro-inflammatory pathway implicated in aggravated tissue damage and delayed healing/recovery, the use of broader and less specific anti-inflammatory interventions in the perioperative period including non-steroidal anti-inflammatory drugs and corticosteroids is common clinical practice.

Preliminary data

Drs. [name] and [name] have studied immune correlates of clinical recovery in patients undergoing hip replacement surgery.^{1,2} They have successfully implemented mass cytometry at the "bedside" to characterize the immune response to surgery close to invivo conditions in peripheral whole blood of patients.²⁵ These studies have been critically supported by our surgeoncollaborator [name] (coinvestigator). In close collaboration with [name] (co-investigator),

[figure not shown]

the team of investigators has developed computational algorithms that allow extracting biologically meaningful and actionable immune parameters from generated high-dimensional data sets.²⁶

Pertinent to this application are data demonstrating that exaggerated signaling in innate immune cells downstream of toll-like receptor 4 (TLR4) shortly after surgery predicts delayed functional recovery and resolution of pain in patients undergoing hip replacement surgery (Figure 1).^{1,2} TLR4 is a major target of HMGB1, which is massively released by tissue trauma.

Data by our collaborator [name] (coinvestigator) demonstrate that oral administration of a high-dose (1,000 mg) versus a very low dose (10 mg control) of coco-flavanol (CocoaVia[®]) in 24 healthy adults (age 50-70 years) significantly suppressed plasma levels of HMGB1 (Figure 2).

Taken together the preliminary data support the main hypothesis that the preemptive administration of cocoa flavanols in patients undergoing surgery will decrease plasma

Page 4 Protocol Version # 1 levels of HMGB1, attenuate signaling activity in innate immune cells downstream of TLR4, and accelerate clinical recovery in patients undergoing joint arthroplasty.

3.0 Study Enrollment and Participation

3.1 Study Enrollment

Participants will be patients undergoing total hip or knee arthroplasty as clinically indicated. Individuals may be referred to this study directly by their orthopedic surgeon, or may be identified in the pre-anesthesia clinic when evaluated for anesthesia care in the context of their scheduled qualifying surgery. A trained study team member, working under the direction of [name], will obtain informed consent prior to any study related activity. Screening will be done via chart review as approved by Stanford's IRB, and by direct participant questioning. No advertising materials will be used

